##### Definition of AE

In a clinical study, an AE is any untoward medical occurrence (i.e., any unfavorable and unintended sign [including abnormal laboratory findings], symptom or disease) in a patient or clinical investigation subject after providing written informed consent for participation in the study. Therefore, an AE may or may not be temporally or causally associated with the use of a medicinal (investigational) product.

In this study, for an event to be classified as an AE, it must be considered to be related to radium-223 dichloride/placebo by the investigator, and ongoing at or occurring from the time of the signing of the ICF and the end of the study. Also classified as AEs (regardless of the investigator's causality assessment) are all occurrences of leukemia, myelodysplastic syndrome, aplastic anemia, primary bone cancer, or any other new primary malignancy; all bone fractures and bone associated events (e.g., osteoporosis) regardless of the investigator's

causality assessment; and, in subjects who receive cytotoxic chemotherapy, all occurrences of febrile neutropenia or hemorrhage.

A surgical procedure that was planned prior to the start of the study by any physician treating the subject should not be recorded as an AE (however, the condition for which the surgery is required may be an AE).

In the following definitions of AEs from the feeder trials, the term “condition” may include abnormal symptoms and diseases.

- Conditions considered to be related to radium-223 dichloride/placebo by the investigator that started before signing of informed consent and for which symptoms or treatment are present after signing of informed consent will be carried over from the feeder trial and documented as AEs.
- Conditions considered to be related to radium-223 dichloride/placebo by the investigator that started or deteriorated after signing of informed consent will be documented as AEs. This includes intercurrent illnesses considered to be related to radium-223 dichloride/placebo by the investigator.

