### 7.5.1.3     Assessments and documentation of adverse events

*Section modified by Amendments 1 (Section 13.1) and 2 (Section 13.2.1.2).*

The investigator has to record on the respective eCRF pages all radium-223 dichloride-/placebo-related AEs ongoing at or occurring from the time of the signing of the ICF and the end of the study. The type of information that should be assessed and recorded by the investigator for each AE is listed in Section 7.5.1.2.

Each event should be described in detail along with start and stop dates (onset and resolution of event), intensity, temporal and causal relationship to feeder trial-related investigational product and / or protocol-related procedures, possible alternative factors (co-morbidities, co-medications), therapeutic action taken, result of therapeutic action, and ultimate outcome of the AE. The investigator's assessment of AEs with grades and causality assessments must be documented and retained in the source documentation.

If more than one radium 223-dichloride- or placebo-related AE occurs, each event should be recorded separately. All AEs and SAEs are to be followed until resolved or as clinically required.

All occurrences of leukemia, myelodysplastic syndrome, aplastic anemia, and primary bone cancer or any other new primary malignancy must be reported as SAEs at any time, and regardless of the investigator's causality assessment. All bone fractures and bone associated events (e.g., osteoporosis) should be collected as either AEs or SAEs if the criteria of SAE were met, regardless of the investigator's causality assessment. If a subject is unable to provide required details for events of interest, this information will need to be obtained from the primary provider.

Adverse events may be reported spontaneously by the subject, the subject's health care professional, or the subject's caregiver, or elicited through questioning during each follow-up telephone call and / or visit during the study. Subject data collected at other standard-of-care visits and / or contacts may be used to satisfy study-required data. As far as possible, all radium-223 dichloride-/placebo-related AEs must be described by their duration (start and stop date), severity (graded according to the NCI-CTCAE, Version 4.03), relationship to treatment, and according to the need of other specific therapy. All information will be recorded in the source documentation and AE eCRF.

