5.1 General Principles

Long-term follow-up data may have been collected within the feeder study, within study 16996, or both. However, only follow-up data (e.g. adverse event data and anti-cancer medication/therapy data) that are collected during study 16996 will be included in the analyses described in this SAP. Limited information from feeder studies will be integrated with study 16996 (Section 5.2.1) to provide summaries of treatment exposure, overall follow-up duration and baseline characteristics at entry into feeder study. As noted in Section 7.2 below, this reduced analysis represents a deviation from the protocol-planned analysis.

Except if otherwise specified, participants will be included in the analyses according to the treatment they received in their feeder trial. Summaries will be presented by indication, feeder study and treatment arm within the feeder study. Listings will be produced by feeder trial arm containing participant data from study 16996, based on the ENR or SAF-LTF set, as applicable.

No formal statistical testing is planned for the overall analysis. The statistical evaluation will be performed by using the software package SAS release 9.4 or higher (SAS Institute Inc., Cary, NC, USA). Data will be analyzed using descriptive statistical methods.

Unless otherwise specified, the following descriptive statistics will be presented in data summaries:

- For continuous or ordinal data, the number of participants with data available (n), arithmetic mean, standard deviation (SD), minimum (min), quartile, median, maximum (max) will be presented.
- For categorical variables, the number of participants and percentage in each category will be presented.

The structure of analysis datasets and layout of analyses and data displays will follow Bayer AG standards, including Therapeutic Area Oncology Standards (TAS) and the Global Medical Standards (GMS), as applicable.

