6.4.2 Adverse Events

Only select categories of post-treatment AEs are to be collected in the long-term follow-up study 16996, including radium-223 dichloride/placebo related AEs and SAEs. The following AE categories identified by the protocol will be evaluated separately:

- New primary malignancies, defined as leukemia, myelodysplastic syndrome, aplastic anemia, primary bone cancer, and any new primary malignancies, regardless of relationship to study drug;
- Bone fractures and bone-associated events:
- Febrile neutropenia and hemorrhage during chemotherapytreatment and for up to 6 months thereafter. A simplified analysis will be performed as specified below
- Pregnancy AEs.

In addition to the above listed select categories of post-treatment AEs collected in study 16996, events related to radium-223 dichloride/placebo by the investigator and ongoing at or occurring from the time of signing of the informed consent and the end of the study were also to be collected by the investigator.

Protocol No.: **BAY 88-8223/16996** Page: 12 of 17

For purposes of the safety analysis of this study, AEs first arising or worsening after signing the 16996 informed consent are defined as 16996-emergent AEs.

AEs will be coded according to the Medical Dictionary for Regulatory Activities (MedDRA) Version 25.1 or higher. When integrating feeder study and 16996 study data, a MedDRA version re-fresh will be performed. The MedDRA version used will be the version in effect per Bayer Standard Operating Procedures (SOPs) at the time of database lock, and will be documented in the study CSR. Differences in MedDRA versions in effect at the time of applicable lock may result in AEs being coded differently between the interim Health Authority reports and the final CSR.

The grade severity of an AE will be documented using the National Cancer Institute (NCI)-Common Terminology Criteria for Adverse Events (CTCAE, Version 4.03).

The set of MedDRA preferred terms (PTs) constituting each category of AEs for analysis purposes will be documented in an appendix to this SAP. The appendix will be approved separately from, and may be approved later than, this SAP.

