Per protocol, febrile neutropenia and hemorrhage AEs are to be collected during and within 6 months of cytotoxic chemotherapy treatment. For the protocol-specified analysis of the incidence of febrile neutropenia or hemorrhage during their chemotherapy treatment and for up to 6 months thereafter, a simplified analysis will be performed, of febrile neutropenia and hemorrhage AEs without regard to cytotoxic chemotherapy association. All 16996-emergent febrile neutropenia and hemorrhage AEs documented in the study CRF will be reported, without regard to chemotherapy treatment.

For the analysis of fractures and bone associated events, separate analyses of patients with bone fractures, patients with bone associated events, and patients with bone fractures and/or bone associated events will be performed. The applicable MedDRA appendix will identify the MedDRA preferred terms applicable to each sub-category.

Unless otherwise specified, the analysis for each AE category will include a summary of the total number and percent of SAF-LTF participants with an AE of the applicable category. Participants with an applicable AE will be summarized by MedDRA preferred term (PT), overall within each applicable MedDRA system organ class (SOC), and overall (any applicable AE), both by worst CTCAE grade and for any grade. For summaries by worst grade, the AE with the worst grade in the applicable summary category will be used. AEs with missing grade will be included in any-grade summaries but not in summaries by worst grade. In addition, listings will be provided.

6.4.2.1 16996-Collected Adverse Events

All AEs collected in study 16996, whether or not collection was required per study 16996 protocol, will be listed for SAF-LTF including AE PT, 16996-emergent (Y/N), start and stop dates, grade, treatment-related (Y/N), serious (Y/N), reason for seriousness, outcome of AE, and time (days) since last dose of study drug. The listing will include all 16996-collected AEs, whether or not emerging within study 16996.

6.4.2.2 16996-Emergent Adverse Events

Summaries of the total number and percent of SAF-LTF participants with an AE of the following categories of 16996-emergent AEs will be presented:

• All 16996-emergent adverse events

Statistical Analysis Plan

Protocol No.: BAY 88-8223/16996

Page: 13 of 17

- Radium-223 dichloride- or placebo-related 16996-emergent AEs;
- Radium-223 dichloride- or placebo-related serious 16996-emergent AEs;

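### The related-AE summaries leave out related events already ongoing and unchanged at 16996 consent, and SAP 7.2 does not say so

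*SAP*

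**What the plan says.** **What counts as an AE.** Protocol 3.2 puts incidence and severity of related AEs first among the primary variables and incidence of related SAEs second, with no limit to new events. On related conditions of earlier onset, Protocol 7.5.1.1 says that any which "started before signing of informed consent and for which symptoms or treatment are present after signing of informed consent will be carried over"; these then become AEs of this study. Protocol 7.5.1.3 has the investigator record related "AEs ongoing at or occurring from the time of the signing of the ICF and the end of the study". SAP 6.4.2 repeats this: related events "ongoing at or occurring from the time of signing of the informed consent and the end of the study were also to be collected".

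**What is summarised.** SAP 6.4.2 states that "AEs first arising or worsening after signing the 16996 informed consent are defined as 16996-emergent AEs". SAP 6.4.2.2 then lists the related summaries as "Radium-223 dichloride- or placebo-related 16996-emergent AEs" and the matching serious events. Of the listing in 6.4.2.1 it says: "The listing will include all 16996-collected AEs, whether or not emerging within study 16996".

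**What is not brought in.** Under SAP 5.1, "only follow-up data (e.g. adverse event data and anti-cancer medication/therapy data) that are collected during study 16996 will be included in the analyses", so feeder-study AE tables do not fill the gap.

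**Follow-up duration.** SAP 5.3 counts the planned period (7 years for mCRPC, 5 for mBC) from the last dose. SAP 6.1.1 starts the combined duration 31 days after the last dose, ends it at the last known alive date, and reports rows from 6 to 84 months without defining a month.

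**The concern.** Emergent tables show new or worse events. They do not show related toxicity that was present at entry and is still there during long-term follow-up, which is part of the long-term safety profile that the study sets out to define. A listing gives the individual records, but no number, percentage, preferred-term count or worst grade by arm.

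Membership of the emergent tables also depends partly on date quality. A carried-over event began before consent by definition, yet Appendix 8.1 makes no exception for it. Two such events can be treated differently only because one start date is complete and the other is not.

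For the follow-up table, a near-empty 84- or 60-month row could be read as poor follow-up when it is an effect of where the clock starts.

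**Working it through.** The plan states no figure to reproduce on this point. The main part is a comparison of texts; the rest is date arithmetic.

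**1. Where an unchanged carried-over related AE goes** (known onset before consent, no worsening)

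| Output | Counted? | Reason |
|---|---|---|
| Related-AE summary, 6.4.2.2 | No | Neither arose nor worsened after consent |
| Related-SAE summary, 6.4.2.2 | No | Same |
| Feeder-study AE tables | Not in this SAP | 5.1 excludes feeder AE data |
| General category analyses, 6.4.2 | Unclear, for fractures and bone events | That text has no emergent limit of its own; 6.4.2.2 names emergent versions |
| Listing, 6.4.2.1 | Yes | Covers all collected AEs, with an emergent flag |

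The general sentence in 6.4.2 promising a summary for each AE category does not clearly rescue related events. It yields to anything specified otherwise, related AEs are not among the four bulleted categories, and 6.4.2.2 specifies emergent.

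**2. Effect of Appendix 8.1.** A completely missing start date is set to the consent date. So is a year-only date in the consent year, and a month-and-year date in the consent month. An earlier year or month stays before consent.

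The documents do not say how often dates are incomplete or how long before consent these events began. For illustration, assume consent dates uniform over the year and onset uniform over the W months before consent.

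- Day missing: share set to consent ≈ 0.5/W, since on average half a month has elapsed. Day-by-day enumeration gives 8.1%, 4.0% and 2.0% for W = 6, 12 and 24.
- Day and month missing: share = 6/W for W ≥ 12, giving 50% and 25% at 12 and 24 months, and about 17% and 12.5% at 36 and 48. For W = 6 it is 0.5 × 0.5 + 0.5 × 1 = 75%. Enumeration gives 74.9%, 49.9% and 24.9% for 6, 12 and 24.
- Full date: 0%. Completely missing: 100%.

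These are shares of events with that kind of date, not of all related events.

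**3. Follow-up rows.** Let w be the final contact's offset from schedule, −28 to +28 days (Protocol Table 7-1), and suppose that contact is the last known alive date.

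- SAP clock: days = years × 365.25 + w − 30, counting both end days.
- Last-dose clock: days = years × 365.25 + w.

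On schedule, 7 years, SAP clock, average month of 365.25/12 = 30.4375 days: (2556.75 − 30)/30.4375 = 83.01.

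| Clock and month | 7 years, w = −28 / 0 / +28 | 5 years, w = −28 / 0 / +28 |
|---|---|---|
| Day 31, average month | 82.1 / 83.0 / 83.9 | 58.1 / 59.0 / 59.9 |
| Day 31, 30-day month | 83.3 / 84.2 / 85.2 | 58.9 / 59.9 / 60.8 |
| Last dose, average month | 83.1 / 84.0 / 84.9 | 59.1 / 60.0 / 60.9 |

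With the day-31 clock and average months, 0 of the 57 window days reach 84 or 60. With calendar months, enumeration over 3,000 last-dose dates also finds none. With 30-day months, 35 of 57 window days reach 84 and 25 of 57 reach 60. From the last dose with average months, 29 of 57 reach each row (w ≥ 0). Leaving out the end day lowers each figure by about 0.03 month.

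**The case against.** The reduced analysis is announced in SAP 1 and 5.1, and 7.2 lists the emergent definition as a change from the protocol. Nothing collected is lost: the listing carries emergent status, dates, grade, relatedness and seriousness. Incidence is commonly read as new or worsening events, and Protocol 8.3.2.1 prescribes no table of events ongoing at consent. All of this stands, which is why the emergent tables should be kept. It does not settle the matter. The protocol expressly makes persisting related conditions AEs of this study, and 7.2 names a definition without saying what that definition removes.

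A reader might infer that these events appear in no summary anywhere. The documents do not support that. The fracture and bone-event text in 6.4.2 is ambiguous enough that a carried-over event of that kind might be counted. The supplemental SAP for Health Authority reports (SAP 5.5) is not available, so nothing can be said about it.

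Appendix 8.1 openly states that it assumes events are emergent whenever possible, which errs toward counting. The shares above rest on assumed onset windows, so they show direction and range only. A companion table has a date problem of its own: it depends on stop dates, and SAP 5.4 allows imputation of AE start dates only. It therefore needs an explicit rule.

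On follow-up, a day-31 start does define a post-treatment period, completion is tabulated separately, and a later known alive date can still reach the row. Moving the clock leaves 28 of 57 window days short with average months, so a footnote is needed either way.

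**Conclusion.** The point holds and should be acted on. Both related-AE summaries omit related events with a known pre-consent onset that persist without worsening, although the protocol counts them as AEs of this study. Within this SAP the 6.4.2.1 listing is the only output sure to show them. How many there are, and how often start dates are incomplete, cannot be estimated from the documents. The emergent restriction is a legitimate, declared choice; what is missing is a statement of its consequence and a count of what it leaves out.

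The follow-up point is secondary and descriptive only. It assumes that the last known alive date is the final in-window contact. Under calendar or average months every such contact misses the row. Under 30-day months on-schedule mCRPC contacts reach 84 while on-schedule mBC contacts miss 60. A reader might infer that AE results or completion figures are distorted. They are not: no AE result uses this duration, and premature discontinuation is counted from the last dose.

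**What to change.** **Related events**
- Keep the 6.4.2.2 emergent summaries.
- Add a clearly labelled companion summary of radium-223/placebo-related AEs, and one of related SAEs, ongoing at or starting after 16996 consent. Present them by system organ class, preferred term and worst recorded grade, noting that the grade may predate consent.
- Include a related event unless its recorded stop date is known to be before consent. Treat missing or ambiguous partial stop dates as ongoing. State this rule alongside SAP 5.4 and Appendix 8.1. Membership then does not depend on imputed start dates.
- Say in 7.2 that the emergent related-AE summaries leave out related events ongoing and unchanged at consent.

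**Follow-up duration (6.1.1)**
- Start the combined duration at the last dose, matching 5.3, and define the month length.
- Keep the 84- and 60-month rows literal. Footnote that contacts early in the ±28-day window fall just short and that completion is shown in the disposition table.

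**Cost.** SAP wording and two table types. SAP 5.1 says "Summaries will be presented by indication, feeder study and treatment arm within the feeder study", so each is repeated at those levels; the number of feeder studies is not given. No new data are needed, since the 6.4.2.1 listing already holds the required fields. The drawbacks are more tables, two kinds of related-AE table to tell apart, and grades that may describe the period before consent.

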6.4.2.3 Deaths

The number and percent of participants with deaths, and the primary cause of death (as reported by the investigator), will be tabulated and listed for SAF-LTFU participants.

Protocol No.: **BAY 88-8223/16996** Page: 14 of 17

7. Document History and Changes in the Planned Statistical Analysis

7.1 Document History

SAP Version	Date	Change	Rationale
1	25 May 2017	Not Applicable	Original version
1 1.1	25 May 2017 01 Apr 2019	Collection and analysis of bone fractures and bone-associated events included Imputation rules for missing AE start dates specified Presentation of systemic anti-cancer medications updated Provision to provide listings in lieu of any tables added, in the event of few reported AEs during 16996	Changes to align the SAP with Amendment 2 of the protocol.
		 Definition of SAF-LTF analysis set 	Additional analysis set for the analysis of 16996-enrolled participants
2	15 FEB 2024	 1. Introduction Specification of duration of follow-up period for breast cancer and prostate cancer studies. Notion no multiple myeloma participants are expected to enter study 16996. 4. Analysis sets Definition of ENR analysis sets Removal of SAF analysis set Description of additional assignment details for participants enrolled in 16996 from non-eligible feeder trials Updated document history table for SAP v1.1 to include SAF-LTF addition 5. General statistical considerations Removal of safety and post-treatment therapy data integration from feeder studies with study 16996 into a longitudinal database Description of limited data (including baseline characteristics and exposure) integration Update and further description of listings presentation 	Additional changes align the SAP with the protocol (Amendment 2), reporting and webposting requirements.

Statistical Analysis Plan

Protocol No · **BAV 88-8223/16996** Page: 15 of 17

I	Protocol No.: BAY 88-8223/16996	Page: 15 of 17
	Definition of premature discontinuation Description of interim safety analyses to meet Health Authority requirements. 6. Statistical methodology Listing of survival assessments Definition of 16996-emergent AEs Description of analyses of safety endpoints and corresponding analysis sets; Additional evaluation of fracture events and incidence of bone-associated events separately Inclusion of demographic and baseline characteristics as well as protocol deviation summaries tables; Specification of categories of AEs for analysis per protocol; Definition of a SAP appendix	Page: 15 of 17
	 Definition of a SAP appendix to include the MedDRA preferred term constituting each category of AE for the safety analyses; Removal of incidence rates and cumulative incidence rates. 	

Consistent use of participants instead of subjects was applied

throughout.

Protocol No.: **BAY 88-8223/16996** Page: 16 of 17

7.2 Changes in Per-Protocol Planned Statistical Analyses

Per the Sponsor decision to perform a reduced and simplified analysis focusing on data from study 16996, the following deviations from the per-protocol planned analyses have been noted in this SAP:

- Section 4. Analysis Sets
 - o Addition of of ENR and SAF-LTF analysis sets
 - o Removal of SAF analysis set;
 - Accounting for the assignment of participants enrolled in 16996 from non-eligible feeder trials.
- Section 5. General Statistical Considerations
 - o Removal of safety data combination between feeder studies and study 16996;
 - Description of limited data integration (including baseline characteristics and exposure);
 - o Description of interim safety analyses to meet Health Authority requirements.
- Section 6. Statistical Methodology
 - Summary of all febrile neutropenia and hemorrhage events collected in study 16996 without regard to chemotherapy treatment;
 - o Definition of 16996-emergent AEs.

Protocol No.: **BAY 88-8223/16996** Page: 17 of 17

